5.5.2. Inclusion criteria

Part 1:

- Male and female children aged >3months and <16 years.
- Clinical diagnosis of severe *P. falciparum* malaria; or parasitological confirmed *P. falciparum* hyperparasitaemia >350,000/ uL.
- Positive malaria test result, by rapid diagnostic test RDT.
- Weight of 5 kg or greater.
- Written informed consent by the parent or guardian.

Part 2:

Study staff and health staff

- Study staff who prepare and administer Artesunate injection to patients in the study or health staff who have not administer the Artesunate injection to patients in the study by themselves

but are either aware of malaria treatment, Artesunate injection, or have observed the treatment provided to severe malaria patients.

- Written informed consent by the study staff and health staff

Study staff for a short video-record

- Study staff who would like to participate in the video record of a procedure to show how 1-step and 2-step Artesunate injections are prepared and administered.
- Written informed consent by the study staff

Policymakers and stakeholders

- Those who are working in the National Malaria Control Program (NMCP) or relevant organizations (WHO, INGOs/NGOs) within the country.
- Written informed consent by the potential participant

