6. PROCEDURES

Part 1

A trial nurse will receive all children who could have severe malaria and are potentially eligible to participate in the study and call the attending physician. The diagnosis of *falciparum* malaria will be made by a PfHRP2-based rapid malaria test. If the test is positive, and there is a clinical judgement that the patient has severe disease (according to a check list provided in the Case Report Forms [CRFs]), the patient can be enrolled, provided written informed consent has been obtained and all eligibility confirmed. The screening sequence will differ for patients with hyperparasitaemia only with no symptoms of severe malaria, as their eligibility will be determined when microscopy results are available, if performed.

Once the patient is enrolled, the randomisation deciding the drug allocation will be carried out. This is done in the following way: The next in a series of numerically sequenced envelopes is opened. The envelope will contain the unique participant number. From the moment the envelope is opened the patient is considered in the study whether or not the protocol is followed correctly thereafter. The envelope contains a slip of paper with a treatment box code number. The treatment box with this code number is then opened.

With the help of the study nurse, the attending physician will take the patient's history, and do a physical exam, where the list in the Case Report Forms (CRFs) serves as a guideline. Parameters include basic demographic parameters, questions regarding the previous history and current history, vital signs, coma score, and others. Patient monitoring during admission: to assure the best possible treatment of each study patient the following variables will be monitored based on WHO guidelines²¹

A detailed monitoring sheet will outline the planned observations and their frequency. In case of abnormal findings staff will be trained to repeat the test and to inform the key decision makers regarding the need to change the management of the patient. To help the treating physician, a practical guideline on the treatment of severe malaria (appendix 4) will be provided to all involved physicians.

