6.5. Follow-up visits

Patients will be asked to come back for a follow-up visit at day 7, 14, 21 and 28. Patients will not be followed up longer. In case of unresolved important sequelae at day 28, the patient will be followed and treated longer in order to provide the appropriate clinical care. All follow up studies procedure will follow appendix 3.

Additional unscheduled visits

Patients presenting to the clinic with a fever or other symptoms on unscheduled days will be assessed by the study physician. Their temperature will be recorded and blood smear will be made for any patient with a documented fever (tympanic temperature $\geq 37.5^{\circ}\text{C}$) or a history of fever. Patients will be treated as clinically indicated.

The monitoring of the patients is not strictly defined in the protocol and should be done according to good medical practice. An exception is monitoring of blood glucose. Blood glucose will be measured on admission and between 4 and 6 hourly thereafter for at least 24 hours or until the patient recovers consciousness and can eat if longer than 24hrs. Blood glucose can be checked at any other time as clinically indicated. The parameters that will be monitored during admission will vary slightly between the study sites, according to different requirements expressed by the IRBs of the different countries. If a patient's clinical situation deteriorates the doctor on call has to be informed immediately. Appropriate steps for the treatment of (complications of) severe malaria are outlined appendix 4.

Time window for follow up visits

The time-window for the visit on Day 7, 14, 21 is +/-3 days and for the visits on Days 28 is -3/+7 days

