7.4 Concomitant Medication

Throughout the study, investigators may prescribe concomitant medications or treatments deemed necessary. Any medication, other than the study medication taken during the study will be recorded in the CRF.

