Dose: Adults and children weighing more 20 kg or more: 60mg is administered at a dose of 2.4mg of artesunate / kg body weight, by intravenous (IV) or intramuscular (IM) injection, at 0, 12 and 24 hours, then once daily until oral treatment can be substituted. Children weighing less than 20 kg: 60mg is administered at a dose of 3 mg of artesunate/kg body weight, by intravenous (IV) or intramuscular (IM) injection, at 0, 12 and 24 hours, then once daily until oral treatment can be substituted (see section 5.1).

New injectable artesunate (Argesun®) 60mg should be administered for a minimum of 24 hours (3 doses), regardless of the patient's ability to tolerate oral medication earlier. After at least 24 hours of Argesun® 60mg and when able to tolerate oral medication, the patient should be switched to a complete treatment course of an oral antimalarial regimen.

Preparation

Because of the instability of artesunate in aqueous solutions, the reconstituted solution must be used within one hour of preparation. Therefore, the required dose of artesunate should be calculated (dose in mg = patient's weight in kg x 2.4 for patients weighing more than 20 kg; or dose in mg = patient's weight in kg x 3 for children weighing less than 20 kg) and the number of vials of artesunate needed

should be determined prior to reconstituting the artesunate powder.

Reconstitution of the artesunate solution Following reconstitution the solution must be diluted according to the method of injection, as described below.

For intravenous (IV) injection & intramuscular (IM) injection (20 mg/ml), using a syringe, withdraw 3 ml of the sodium bicarbonate and arginine solvent, which is half the volume of the ampoule, and inject this into the vial containing the artesunate powder. Gently shake the vial for up to 3-5 minutes or until the powder is completely dissolved and the solution is clear. If the solution appears cloudy or a precipitate is present, it should be discarded. The reconstituted artesunate solution should always be used immediately, and discarded if not used within one hour. The end concentration of the solution will be 20 mg artesunate per ml solvent. Thus, the volume in ml for administration to the patient will be equal to: $(\text{desired dose in mg})/20$

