APPENDIX 4. TREATMENT GUIDELINES FOR SEVERE MALARIA

Introduction

Severe *falciparum* malaria is a medical emergency. Mortality is high and most deaths occur within 24 hours after admission to the hospital. Cerebral malaria, the most prominent manifestation of severe malaria carries a 16-20% mortality, but once multiple vital organ dysfunction occurs, the figure increases to as high as 30% (WHO 1990, 2000). The clinical manifestations depend on age. Hypoglycaemia, convulsions, and severe anaemia are relatively more common in children; acute renal failure, jaundice, and the acute respiratory distress syndrome (ARDS) are more common in adults. Cerebral malaria (with coma) and a severe metabolic (lactate) acidosis may occur at any age, and the severity of both features is a strong prognostic factor for a fatal outcome.

Cerebral malaria is characterized by coma of varying depth, usually with no focal signs. Convulsions occur in up to 80% of cases in children, but in less than 10% of adults. If the patient survives, there are usually (>90%) no neurological sequelae. Unlike in septicaemia, circulatory shock ('algid malaria') is not common in severe malaria. If hypotension is present, one should consider concomitant (gram negative) septicaemia or meningitis. Also, leucocytosis is not common in malaria, although it can be present in very severe disease. Leucocytosis with a shift to the left, should trigger the possibility of concomitant bacterial infection. Thrombocytopenia is always present in severe malaria, but this is seldom accompanied by bleeding problems. Diffuse intravascular coagulation (DIC) is rare (less than 5% of severe cases), and can cause serious bleeding. Black water fever is a rare complication of *falciparum* malaria, with severe intravascular haemolysis and haemoglobinuria. It is associated with the use of quinine and G-6-PD deficiency. About 10% of these patients have oliguric renal failure (Tran 1996). Table 1 gives a brief summary of the manifestations of severe malaria.

Diagnosis and differential diagnosis

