Hypoglycaemia as a cause for convulsions should be ruled out. A lumbar puncture should be considered. The usual nursing care for the unconscious patient should be applied. If available a nasogastric tube should be inserted and the stomach contents let out. To decrease the chances of aspiration, enteral feeding should not be started on the first day of admission. The patient should be turned every 2 hours to prevent bedsores. If possible, it is preferable to insert a urethral ('Foley') catheter to prevent maceration of the skin and for monitoring fluid management. Eyes should be kept irrigated with saline or artificial tears and the lids kept closed with eye pads. The severity of coma should be graded using the Glasgow coma scale for adults and the Blantyre coma scale for children. Deterioration in the coma score should be reported immediately to the physician on call.

Convulsions are very common in children with cerebral malaria. As for coma, hypoglycaemia as a cause for convulsions should be ruled out. A lumbar puncture should be considered. In adults, convulsions are relatively rare, so that prophylaxis is not generally recommended. If seizures occur, they should be treated promptly with intravenous benzodiazepines (adults 10 mg iv, children 0.3 mg/kg). Since children are prone to febrile convulsions, treatment to reduce fever (paracetamol, cold sponging, etc.) should be given if the rectal temperature is above 39°C.

Hypoglycaemia is particularly common in children and pregnant women with malaria, and, as mentioned above, with the use of quinine. It can be treated with 1 ml/kg of a 50% glucose solution.

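### The seizure-dose line in Appendix 4 has no paediatric maximum, so above 33.3 kg the child dose exceeds the adult dose printed beside it

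*Protocol*

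**What the plan says.** The paragraph on convulsions in Protocol Appendix 4 states that if seizures occur, "they should be treated promptly with intravenous benzodiazepines (adults 10 mg iv, children 0.3 mg/kg". It gives a fixed dose for adults and a weight-based dose for children. It sets no maximum for the child dose and no age or weight at which the adult dose takes over. Table 1 of the same appendix lists diazepam, phenobarbitone and phenytoin for convulsions, without doses. No other section of the protocol or SAP gives a limit.

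Protocol section 5.5.2 admits to Part 1 "Male and female children aged >3months and <16 years", with "Weight of 5 kg or greater" as the only weight criterion. The exclusion criteria in section 5.5.3 add no upper weight limit.

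Two sections direct physicians to the appendix. Section 6 says that "a practical guideline on the treatment of severe malaria (appendix 4) will be provided to all involved physicians", and section 6.5 says "Appropriate steps for the treatment of (complications of) severe malaria are outlined appendix 4". Section 7.4 makes clear that the guidance does not bind: "investigators may prescribe concomitant medications or treatments deemed necessary".

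**The concern.** A dose per kilogram with no maximum keeps rising with weight, while the adult dose in the same parenthesis is fixed. At some weight the child dose must overtake the adult dose. If eligible children can weigh more than that, the line tells the physician to give a large child more drug than an adult would get.

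The line also allows two readings. Every Part 1 patient is a child by the trial's own criteria, so the literal reading applies 0.3 mg/kg to all of them. A physician could equally treat a well-grown 15-year-old as an adult and give 10 mg. Appendix 4 does not settle which is meant. For the study drug, Appendix 1 does state where children join the adult schedule: its 2.4 mg/kg dose is for "Adults and children weighing more 20 kg or more".

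What is at stake is the clarity of an emergency dose. The introduction to Appendix 4, in its paragraph on cerebral malaria, says "Convulsions occur in up to 80% of cases in children, but in less than 10% of adults". The appendix asks for prompt treatment, so the dose should not need interpreting at the bedside.

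**Working it through.** The plan states no crossing weight and no maximum, so there is no figure of its own to reproduce. The check is simple arithmetic on the printed doses.

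**Inputs**

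- Adult dose: 10 mg (Protocol Appendix 4, convulsions).
- Child dose: 0.3 mg/kg, no maximum printed (same sentence).
- Weight at entry: 5 kg or more, no upper limit (Protocol sections 5.5.2 and 5.5.3).
- Age at entry: over 3 months and under 16 years (Protocol section 5.5.2).
- Weights other than 5 kg in the table below are illustrative, because the documents give no weight distribution.

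**Step 1: where the two doses meet**

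Crossing weight = adult dose / child dose per kg = 10 / 0.3 = 33.3 kg.

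**Step 2: the child dose by weight, and its excess over the adult dose**

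Literal child dose = 0.3 × weight. Excess = literal child dose − 10 mg. Percentage excess = excess / 10.

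| Weight (kg) | Literal child dose (mg) | Adult dose (mg) | Excess over adult dose | Child dose if limited to 10 mg |
|---|---|---|---|---|
| 5 | 1.5 | 10 | none | 1.5 |
| 30 | 9.0 | 10 | none | 9.0 |
| 33 | 9.9 | 10 | none | 9.9 |
| 34 | 10.2 | 10 | 0.2 mg (2%) | 10 |
| 40 | 12.0 | 10 | 2 mg (20%) | 10 |
| 50 | 15.0 | 10 | 5 mg (50%) | 10 |

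**Step 3: effect of a limit**

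Taking the smaller of 0.3 × weight and 10 mg leaves every dose at or below 33.3 kg unchanged. Above that weight the child and adult readings both give 10 mg, so their difference is zero and the start of adulthood no longer matters. Per kilogram, the limited dose is 10/34 = 0.29 mg/kg at 34 kg, 10/40 = 0.25 mg/kg at 40 kg and 10/50 = 0.20 mg/kg at 50 kg.

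**Step 4: whether eligible patients can be above the crossing weight**

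Neither the inclusion nor the exclusion criteria prevent it. How many will be above 33.3 kg cannot be estimated from the documents.

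**The case against.** The strongest objection is that the documents do not supply the safety premise. An unlimited mg/kg dose is a hazard only if 10 mg is a ceiling, and the protocol does not say so or show harm above it. What the text establishes is narrower: two printed doses cross, and the line does not say which prevails. That limitation stands, and it is why the clinical team should confirm the maximum.

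Second, Appendix 4 is general guidance that also covers adults, and section 7.4 leaves concomitant treatment to the investigator. A physician sees the adult dose in the same parenthesis and may well stop there. This is fair and lowers the priority. It does not make the line coherent for those who follow it as written.

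Third, few patients may be affected. A child must weigh more than 33.3 kg, have a seizure, and be dosed literally. The 80% figure comes from the cerebral malaria paragraph and concerns children generally, whereas the trial enrols all forms of severe malaria and also hyperparasitaemia alone. It shows that convulsions matter in this age group but gives no rate for heavier children.

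Fourth, the comparison with the study drug is imperfect. Appendix 1 states 20 kg because the artesunate dose per kilogram changes there, and it prints no absolute maximum either. It shows that the protocol marks a child-to-adult boundary where it considers one necessary. It does not show that the protocol usually limits doses.

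Fifth, the sentence names a drug class, and a maximum dose is specific to a drug. That ambiguity is real and deserves its own query. It does not block this change, because the limit attaches to whichever benzodiazepine the printed 10 mg already refers to. Other lines in Appendix 4 are equally terse, for example glucose at 1 ml/kg without a maximum. This line differs in that it prints two doses that conflict for eligible patients.

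**Conclusion.** The concern holds as a minor correction. Followed literally, the seizure line gives any enrolled child above 33.3 kg more than the adult dose beside it: 2% more at 34 kg, 20% more at 40 kg and 50% more at 50 kg. At or below 33.3 kg there is no problem.

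The conclusion rests on reading the child dose as applying to all Part 1 patients, on the absence of an upper weight limit, and on the absence of a maximum anywhere in either document. It does not rest on any claim that more than 10 mg is harmful. The guidance is the same in both arms, so the comparison of formulations, the endpoints, the sample size and the analysis are unaffected.

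**What to change.** In the convulsions paragraph of Protocol Appendix 4, extend the child dose to read: *children 0.3 mg/kg, not exceeding the adult dose of 10 mg*. The clinical team should confirm that 10 mg is the maximum they intend before the text is changed. Leave the reference to the drug class as it stands, and ask the clinical team separately which benzodiazepine the doses refer to.

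The cost is one phrase in an appendix and a short clinical check. Nothing in the statistical plan needs to change.

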Intravenous vs. Intramuscular Results.....	7
Analytical Issues.....	10
Record Keeping.....	10
Appendices	10

METHODOLOGY

STUDY DESIGN

This was a pharmacokinetic cross-over study evaluating a new parenteral formulation of intravenous (IV) and intramuscular (IM) artesunate, and the currently used parenteral formulation of artesunate.

A total of 72 male and female healthy subjects were enrolled and completed all drug administration arms and sampling according to the protocol. The study comprised of 39 male (54.2%) and 33 female (45.8%) volunteers, with a median (range) age of 35 (21- 53) years and body weight of 58.55 (44.3-82.3) kg. All participants received 2.4 mg/kg of the new parenteral formulation of artesunate (test formulation, T) and the currently used parenteral formulation of artesunate (reference formulation, R) both IV and IM, in a randomised four-period cross-over design.

Blood samples for plasma artesunate and dihydroartemisinin quantification were collected at: pre-dose, 5 min, 15 min, 30 min, 45 min, 1 hr, 1.5 hr, 2 hr, 3 hr, 4 hr, 6 hr, 8 hr, 12 hr and 24 hr post dose in all patients, in all drug administration arms.

DRUG ANALYSIS

The drug analysis was performed at the department of clinical pharmacology, Mahidol-Oxford Tropical Medicine Research Unit, Thailand (see bioanalytical drug analysis report AR03_18002_ARS v.2 for more information). The laboratory is ISO-accredited for competency (ISO 15189:2012) and safety (ISO 15190:2003). All quality control samples were within regulatory acceptance limits ($\pm 15\%CV$).

PHARMACOKINETIC ANALYSIS

Individual concentration-time data were evaluated using non-compartmental analysis in Phoenix 64 version 8.1 (Certara, Princeton, New Jersey, USA). Total exposure up to the last measured concentration (AUC_{0-LAST}) was calculated using the linear trapezoidal method for ascending concentrations and the logarithmic trapezoidal method for descending concentrations. Drug exposure was extrapolated from the last observed concentration to time infinity by C_{LAST}/λ_Z for each individual subject to compute total drug exposure ($AUC_{0-\infty}$). The terminal elimination half-life ($t_{1/2}$) was estimated by log-linear regression (best fit option) of the observed concentrations in the terminal elimination phase. Maximum concentration (C_{MAX}) and time to maximum concentration (T_{MAX}) were taken directly from the observed data. Apparent volume of distribution (V) and elimination clearance (CL) were computed individually according to standard procedures in Phoenix. Artesunate and dihydroartemisinin were evaluated separately, and also combined by adding the molar concentrations of artesunate and dihydroartemisinin (at each time point) for each individual before pharmacokinetic evaluation.

As a secondary analysis the intramuscular bioequivalence of artesunate and dihydroartemisinin exposures were evaluated comparing the IM test formulation and the IV test formulation.

STATISTICAL ANALYSIS

Ln-transformed pharmacokinetic exposure parameters (C_{MAX} , AUC_{0-LAST} and $AUC_{0-\infty}$) were evaluated with the bioequivalence function in Phoenix 64 to assess the bioequivalence of drug formulations. Study arm was used as “*formulation input*”, subject ID was used as “*subject input*”, individual sequence of the four administrations was used as “*sequence input*” (e.g. TIM RIV TIV RIM), and individual study occasion visit as “*period input*” (ranging from 1 to 4) in the bioequivalence function. Bioequivalence was assumed if the 90% confidence intervals of the ratio (test formulation/reference formulation) of C_{MAX} , AUC_{0-LAST} and $AUC_{0-\infty}$ fell within 80% to 125%. The 90% confidence interval of this ratio was calculated according to the equation below. If the administered doses of the test and reference formulation deviated with more than 5% within a subject, the above analysis was carried out with dose normalised parameter values.

Bioequivalence is computed by Phoenix 64 as follow:

$$\text{Mean ratio (\%)} = 100 \times e^{\text{Parameter}_{\text{Test}} - \text{Parameter}_{\text{Reference}}}$$

where $\text{Parameter}_{\text{Test}}$ and $\text{Parameter}_{\text{Reference}}$ are the least square mean of the natural logarithm of parameters derived for the test and reference formulation, respectively. The upper and lower boundary of the 90% confidence interval are calculated as follow:

$$90\% \text{ Confidence Interval} = 100 \times e^{(\text{Parameter}_{\text{Test}} - \text{Parameter}_{\text{Reference}}) \pm (t_{0.95} \times SE_D)}$$

where $t_{0.95}$ is taken from the student-t distribution, SE_D is the standard error of the difference of the test and reference least squares means.

PHARMACOKINETIC RESULTS SUMMARY

Dose normalisation was not performed because all administered doses of artesunate (test and reference formulations) were within $\pm 5\%$ for each patient. Table 1-9 present the bioequivalence results. All other results and associated data are presented in appendices 1, 2 and 3 below. Each appendix contain raw data, Phoenix 64 user settings for the analysis, result graphs, and tabulated pharmacokinetic parameter estimates. The appendices 1, 2, and 3 report “*IV test vs. IV reference*”, “*IM test vs. IM reference*”, and “*IV test vs. IM test*” results separately.

ARTESUNATE RESULTS

Bioequivalence could be concluded for the parent drug, artesunate, for total exposure but not for maximum concentration when administered IV (Table 1). Bioequivalence was demonstrated for all parameters for artesunate when administered IM (Table 4).

DIHYDROARTEMISININ RESULTS

Parenteral administration of test and reference formulations showed matching exposures to the active metabolite, dihydroartemisinin, and bioequivalence of the test formulation could be demonstrated both when administered IV (Table 2) and IM (Table 5).

COMBINED ARTESUNATE AND DIHYDROARTEMISININ RESULTS

Parenteral administration of test and reference formulations showed matching exposures to the combined exposure to artesunate and dihydroartemisinin, and bioequivalence of the test formulation could be demonstrated both when administered IV (Table 3) and IM (Table 6).

INTRAVENOUS VS. INTRAMUSCULAR RESULTS

As expected bioequivalence could not be concluded for the maximum concentration of artesunate and dihydroartemisinin when comparing IV and IM administration of the test formulation, due to systematically lower peak levels of both compounds after IM administration. Furthermore, total exposure to artesunate was consistently higher after IM administration, compared to IV administration, and bioequivalence could not be concluded for artesunate (Table 7). However, bioequivalence was demonstrated for the total exposure to dihydroartemisinin (Table 8). Bioequivalence was demonstrated for the combined exposure to artesunate and dihydroartemisinin for the IM formulation, but not for the maximum concentration (Table 9).

Table 1. Bioequivalence of artesunate when administered intravenously

Parameter	Ratio (%)	CI 90% Lower	CI 90% Upper
Ln(C_{MAX})	81.50	74.74	88.87
Ln(AUC_{0-LAST})*	85.85	80.09	92.02
Ln($AUC_{0-\infty}$)*	85.87	80.11	92.05

Test: IV test formulation; Reference: IV reference formulation.

Ratio is the geometric mean ratio between the test and reference formulation (Test/Reference); CI 90% Lower is the lower boundary of the geometric 90% confidence interval; CI 90% Upper is the upper boundary of the geometric 90% confidence interval; Ln is the natural logarithm; C_{MAX} is the maximum concentration; AUC_{0-LAST} is the area under the concentration-time curve from time zero to the last observation; $AUC_{0-\infty}$ is the area under the concentration-time curve from time zero to infinity.

* Indicates that the criterion for bioequivalence is fulfilled, i.e. the CI 90% of the ratio (test/reference) is within 80-125%.

Table 2. Bioequivalence of dihydroartemisinin when administered intravenously

Parameter	Ratio (%)	CI 90% Lower	CI 90% Upper
Ln(C _{MAX})*	100.18	92.63	108.35
Ln(AUC _{0-LAST})*	98.56	95.44	101.77
Ln(AUC _{0-∞})*	98.54	95.40	101.78

Test: IV test formulation; Reference: IV reference formulation.

Ratio is the geometric mean ratio between the test and reference formulation (Test/Reference); CI 90% Lower is the lower boundary of the geometric 90% confidence interval; CI 90% Upper is the upper boundary of the geometric 90% confidence interval; Ln is the natural logarithm; C_{MAX} is the maximum concentration; AUC_{0-LAST} is the area under the concentration-time curve from time zero to the last observation; AUC_{0-∞} is the area under the concentration-time curve from time zero to infinity.

* Indicates that the criterion for bioequivalence is fulfilled, i.e. the CI 90% of the ratio (test/reference) is within 80-125%.

Table 3. Bioequivalence of combined artesunate and dihydroartemisinin when administered intravenously

Parameter	Ratio (%)	CI 90% Lower	CI 90% Upper
Ln(C _{MAX})*	86.71	81.43	92.33
Ln(AUC _{0-LAST})*	95.17	92.38	98.04
Ln(AUC _{0-∞})*	95.18	92.39	98.05

Test: IV test formulation; Reference: IV reference formulation.

Ratio is the geometric mean ratio between the test and reference formulation (Test/Reference); CI 90% Lower is the lower boundary of the geometric 90% confidence interval; CI 90% Upper is the upper boundary of the geometric 90% confidence interval; Ln is the natural logarithm; C_{MAX} is the maximum concentration; AUC_{0-LAST} is the area under the concentration-time curve from time zero to the last observation; AUC_{0-∞} is the area under the concentration-time curve from time zero to infinity.

* Indicates that the criterion for bioequivalence is fulfilled, i.e. the CI 90% of the ratio (test/reference) is within 80-125%.

Table 4. Bioequivalence of artesunate when administered intramuscularly

Parameter	Ratio (%)	CI 90% Lower	CI 90% Upper
Ln(C _{MAX})*	110.74	104.50	117.35
Ln(AUC _{0-LAST})*	106.47	103.84	109.16
Ln(AUC _{0-∞})*	106.43	103.80	109.12

Test: IM test formulation; Reference: IM reference formulation.

Ratio is the geometric mean ratio between the test and reference formulation (Test/Reference); CI 90% Lower is the lower boundary of the geometric 90% confidence interval; CI 90% Upper is the upper boundary of the geometric 90% confidence interval; Ln is the natural logarithm; C_{MAX} is the maximum concentration; AUC_{0-LAST} is the area under the concentration-time curve from time zero to the last observation; AUC_{0-∞} is the area under the concentration-time curve from time zero to infinity.

* Indicates that the criterion for bioequivalence is fulfilled, i.e. the CI 90% of the ratio (test/reference) is within 80-125%.

PHARMACOKINETIC REPORT PKR_102 v.2

Issue date: 25 Mar 2019

Page 9/11

Table 5. Bioequivalence of dihydroartemisinin when administered intramuscularly

Parameter	Ratio (%)	CI 90% Lower	CI 90% Upper
Ln(C _{MAX})*	107.32	102.35	112.53
Ln(AUC _{0-LAST})*	105.12	102.20	108.13
Ln(AUC _{0-∞})*	105.13	102.22	108.12

Test: IM test formulation; Reference: IM reference formulation.

Ratio is the geometric mean ratio between the test and reference formulation (Test/Reference); CI 90% Lower is the lower boundary of the geometric 90% confidence interval; CI 90% Upper is the upper boundary of the geometric 90% confidence interval; Ln is the natural logarithm; C_{MAX} is the maximum concentration; AUC_{0-LAST} is the area under the concentration-time curve from time zero to the last observation; AUC_{0-∞} is the area under the concentration-time curve from time zero to infinity.

* Indicates that the criterion for bioequivalence is fulfilled, i.e. the CI 90% of the ratio (test/reference) is within 80-125%.

Table 6. Bioequivalence of combined artesunate and dihydroartemisinin when administered intramuscularly

Parameter	Ratio (%)	CI 90% Lower	CI 90% Upper
Ln(C _{MAX})*	111.29	106.24	116.58
Ln(AUC _{0-LAST})*	105.38	102.98	107.82
Ln(AUC _{0-∞})*	105.39	103.01	107.83

Test: IM test formulation; Reference: IM reference formulation.

Ratio is the geometric mean ratio between the test and reference formulation (Test/Reference); CI 90% Lower is the lower boundary of the geometric 90% confidence interval; CI 90% Upper is the upper boundary of the geometric 90% confidence interval; Ln is the natural logarithm; C_{MAX} is the maximum concentration; AUC_{0-LAST} is the area under the concentration-time curve from time zero to the last observation; AUC_{0-∞} is the area under the concentration-time curve from time zero to infinity.

* Indicates that the criterion for bioequivalence is fulfilled, i.e. the CI 90% of the ratio (test/reference) is within 80-125%.

Table 7. Bioequivalence of artesunate when administered intramuscularly and intravenously

Parameter	Ratio (%)	CI 90% Lower	CI 90% Upper
Ln(C _{MAX})	24.16	22.43	26.02
Ln(AUC _{0-LAST})	164.95	154.83	175.73
Ln(AUC _{0-∞})	165.16	155.02	175.95

Test: IM test formulation; Reference: IV test formulation.

Ratio is the geometric mean ratio between the test and reference formulation (Test/Reference); CI 90% Lower is the lower boundary of the geometric 90% confidence interval; CI 90% Upper is the upper boundary of the geometric 90% confidence interval; Ln is the natural logarithm; C_{MAX} is the maximum concentration; AUC_{0-LAST} is the area under the concentration-time curve from time zero to the last observation; AUC_{0-∞} is the area under the concentration-time curve from time zero to infinity.

* Indicates that the criterion for bioequivalence is fulfilled, i.e. the CI 90% of the ratio (test/reference) is within 80-125%.

PHARMACOKINETIC REPORT PKR_102 v.2

Issue date: 25 Mar 2019

Page 10/11

Table 8. Bioequivalence of dihydroartemisinin when administered intramuscularly and intravenously

Parameter	Ratio (%)	CI 90% Lower	CI 90% Upper
Ln(C _{MAX})	43.74	40.43	47.33
Ln(AUC _{0-LAST})*	91.55	88.40	94.81
Ln(AUC _{0-∞})*	91.60	88.46	94.86

Test: IM test formulation; Reference: IV test formulation.

Ratio is the geometric mean ratio between the test and reference formulation (Test/Reference); CI 90% Lower is the lower boundary of the geometric 90% confidence interval; CI 90% Upper is the upper boundary of the geometric 90% confidence interval; Ln is the natural logarithm; C_{MAX} is the maximum concentration; AUC_{0-LAST} is the area under the concentration-time curve from time zero to the last observation; AUC_{0-∞} is the area under the concentration-time curve from time zero to infinity.

* Indicates that the criterion for bioequivalence is fulfilled, i.e. the CI 90% of the ratio (test/reference) is within 80-125%.

Table 9. Bioequivalence of combined artesunate and dihydroartemisinin when administered intramuscularly and intravenously

Parameter	Ratio (%)	CI 90% Lower	CI 90% Upper
Ln(C _{MAX})	26.62	25.05	28.29
Ln(AUC _{0-LAST})*	102.10	98.59	105.73
Ln(AUC _{0-∞})*	102.06	98.55	105.69

Test: IM test formulation; Reference: IV test formulation.

Ratio is the geometric mean ratio between the test and reference formulation (Test/Reference); CI 90% Lower is the lower boundary of the geometric 90% confidence interval; CI 90% Upper is the upper boundary of the geometric 90% confidence interval; Ln is the natural logarithm; C_{MAX} is the maximum concentration; AUC_{0-LAST} is the area under the concentration-time curve from time zero to the last observation; AUC_{0-∞} is the area under the concentration-time curve from time zero to infinity.

* Indicates that the criterion for bioequivalence is fulfilled, i.e. the CI 90% of the ratio (test/reference) is within 80-125%.

ANALYTICAL ISSUES

Three subjects (ID 122, 224, and 321) discontinued to study before completion, and were replaced. Pharmacokinetic data for these three individuals are not reported here.

RECORD KEEPING

The Phoenix 64 projects will be saved and stored together with the raw data in electronic form on the MORU server (Bowmore).

APPENDICES

